Each of the twenty-two 90-min lab sessions will begin with 15 minutes of the treating therapist observing the participant performing the exercise they do at home, reinforcing instructions, and troubleshooting any problems, followed by 75 minutes of instructing and guiding the participants in practicing functional tasks with their paretic hand. Tasks will involve using the paretic hand to pick up, manipulate, and release objects commonly used in daily life. The treating therapist will adjust task difficulty from easy-to-acquire-and-manipulate tasks to tasks requiring wider hand opening, greater

complexity and skill, graded hand opening (release), and coordination of hand function with proximal upper limb movement. The pace and content of the therapy will be standardized via study-specific protocols and task lists. The CCFES group will use CCFES to assist the paretic hand in performing tasks. The cNMES group will practice tasks using their paretic hand but without any stimulation because cNMES is not amenable to assisting with tasks since it is not controlled by the patient (one of the unique advantages of CCFES). Therefore, to ensure that both groups receive an equal weekly duration of electrical stimulation, the cNMES group will have longer home stimulation exercise sessions than the CCFES group (see treatment regimens above). The TOT group will receive the same task practice as the cNMES group (i.e., no stimulation). For subjects with severe hand impairment, early task practice sessions will focus on simpler tasks, such as opening the hand adequately to acquire a small object. If it is not possible to perform tasks, then the therapist will focus on passive and active-assisted range of motion, arm placement activities in preparation for hand tasks, and hand placement on target surfaces and objects.

Adherence to the home stimulation regimen will be monitored with participant diaries and electronic data logging by the stimulator at every visit during the treatment period. The stimulator logs the date and time the unit is turned on and off and the start and completion of exercise periods. All participants will also be given a diary to log completion of sessions. The diaries will be reconciled with electronic data logs at every lab session, in the presence of the participant to encourage adherence.

Outcome Measures

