Blinded assessments will take place at baseline, mid-treatment(6 wk), end-of-treatment (12 wk), and at 3- and 6-months post-treatment. All assessments will be done with no electrical stimulation. Subjects will refrain from using their stimulators for 24 hours prior to their 6-week and 12-week assessments in order to avoid any transient carry over effects or muscle fatigue.

Box and Blocks Test (BBT): The primary endpoint is change in dexterity at 6-monthspost-treatment, as assessed by the BBT. The BBT is a measure of manual dexterity, which requires the subject to pick up one block at a time, move it over a partition, and release it in a target area as many times as

possible in 60 seconds. Participants will perform the test first with the unaffected hand, and then with the affected hand. The BBT is classified as an activity (ICF domain) measure by the Rehabilitation Measures Database and the Evidence-Based Review of Stroke Rehabilitation.

Upper Extremity Fugl-Meyer Assessment (UEFM). The UEFM is a measure of post-stroke upper limb motor impairment that takes into account synergy patterns, isolated strength, coordination, and hypertonia. Volitional movement of the upper limb (shoulder, elbow, forearm, wrist, and hand) is examined in and out of synergies. Each item is graded on a 3-point ordinal scale (0, cannot perform; 1, perform partially; and 2, perform fully) and summed to provide a maximum score of 66.

Action Research Arm Test, (ARAT): The ARAT is a measure of upper extremity functional ability. The ARAT is a 19-item test divided into four categories (grasp, grip, pinch, and gross movement), with 16 of the 19 ARAT items measuring distal regions of the arm, making it an ideal and sensitive measure for this distally based intervention.

Stroke Upper Limb Capacity Scale (SULCS). The SULCS is a 10-item test in which stroke patients are rated using a 2-point ordinal scale on their performance of upper limb tasks ranging from reaching forward to manipulating coins. It is a valid and reliable measure of upper limb capacity that is suitable for a wide range of patients including those with poor hand-related upper limb capacity.

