Questionnaires. The subjects' impressions of the effectiveness of the intervention, the dose, and the ease of using the device/equipment will be captured with questionnaires including the Stroke Impact Scale Hand Section, the Neuro-QOL Upper Extremity Function Fine Motor ADL from the Patient Reported Outcomes Measurement Information System (PROMIS) Neuro-QOL Bank, and an end-of-treatment questionnaire. The purpose is to gain insight into how well the device and dosage are tolerated and the subjects' perception of effectiveness. The questionnaires will be administered at end of treatment by a staff member who will have no other interaction with the subjects.

Other Measures. Additional secondary measures include changes in muscle tone (modified Ashworth scale) and finger flexion and extension strength (dynamometry). These outcomes along with the

baseline characteristics collected and treatment adherence may provide insight into mechanisms of action and interpretation of the main findings.

Experimental Flow

Participation time for each subject will be ~9.5 months (inc. 3 months treatment, 6months follow-up).

There are a total of 29 visits involved in this study.

Visit 1. Consent and eligibility (2 hrs)

Visit 2. Baseline Assessment (2 hrs)

Visit 3. Randomization, Device Setup and Training (2 hrs)

Visits 4-14. Therapy Visits (1.5 hrs)

Visit 15. Mid-Treatment Outcome Assessment (2 hrs)

Visits 16-26. Therapy Visits (1.5 hrs)

Visit 27. End of Treatment Outcome Assessment (2 hrs)

Visit 28. 3-mo post-Treatment Outcome Assessment (2 hrs)

Visit 29. 6-mo post-Treatment Outcome Assessment (2 hrs)

Selection Criteria

Inclusion Criteria

- Age 21 to 90 years old at time of randomization
- 6 to 24 months since a first clinical cortical or subcortical, ischemic or hemorrhagic stroke
- unilateral upper limb hemiparesis with finger extensor strength of \leq grade 4/5 on the Medical Research Council (MRC) scale
- score of $\geq 1/14$ and $\leq 11/14$ on the hand section of the upper extremity Fugl-Meyer Assessment
- adequate active movement of shoulder and elbow to position the paretic hand in the workspace for table-top task practice
- able to follow 3-stage commands
- able to recall at least 2 of a list of 3 items after 30 minutes
- skin intact on hemiparetic arm

- surface electrical stimulation of the paretic finger and thumb extensors produces functional hand opening without pain (this will exclude patients who have too much flexor spasticity)

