* Uncomfortable Sensation – Electrical stimulation of a muscle may be perceived as a twitching or vibrating sensation and may be uncomfortable. Electrical stimulation of a nerve may be perceived as a strong but short shock and may be uncomfortable. Electrical stimulation of the skin may be perceived as a “pins and needles” sensation and may be uncomfortable. Discomfort is common but stimulus parameters will be adjusted to the subject’s comfort.

* Electrical Hazards – There is a possibility of an electrical shock hazard whenever electrical stimulation is used or whenever electrical equipment is used to make measurements. There is a possibility of an electrical burn whenever electrical stimulation with surface electrodes is used. The equipment to be used has been designed and tested to minimize these risks. Subjects will be trained how to use the stimulator safely and will be asked to adhere to a list of safety precautions. With these precautions, electrical hazards are rare.

* Stimulator Malfunction – There is a rare possibility that the stimulator may malfunction and produce painful stimulation after it has been programmed in the laboratory. The subject could feel a sudden burning sensation, which can damage the skin if it does not stop. The equipment to be used has been designed and tested to minimize this risk. If the subject experiences pain from the stimulation, they will be told to turn off the stimulator and/or unplug the electrode cables, stop using it, and contact study personnel.

* Unknown Effect of Stimulation on Pregnancy – The effect of electrical stimulation on a fetus is not known. If the subject is pregnant or is planning to become pregnant they may not participate in this

study. Subjects will be told to notify study personnel if they suspect that they become pregnant during the study.

All Groups

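### The tolerability questionnaire is given only at week 12, with no provision for participants who leave earlier, so its results can overstate tolerability

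*Combined protocol and SAP*

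**What the plan says.** The Questionnaires paragraph (protocol, Outcome Measures) covers participants' views of effectiveness, dose and ease of use of the equipment. It gives the aim as follows: "The purpose is to gain insight into how well the device and dosage are tolerated". The timing is in the next sentence: "The questionnaires will be administered at end of treatment by a staff member who will have no other interaction with the subjects".

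The opening of Outcome Measures fixes what end of treatment means in the schedule: "end-of-treatment (12 wk), and at 3- and 6-months post-treatment". Experimental Flow lists the matching assessment as Visit 27 and states: "There are a total of 29 visits involved in this study". None of the listed visits is an early-termination visit.

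Other parts of the protocol also bear on tolerability:

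- Potential Risks says of stimulation: "Discomfort is common but stimulus parameters will be adjusted to the subject’s comfort".
- Risk Management asks participants to report any listed risk promptly, and allows electrodes to be changed or stimulation to be paused.
- Methods and Procedures has the therapist watch the home exercise at the start of each lab session, "reinforcing instructions, and troubleshooting any problems". Diaries and stimulator logs are reviewed at every treatment-period visit.

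The Statistical Analysis Plan describes no tolerability or adverse-event analysis. Its primary sample is limited to participants who finished the treatment phase. Its all-randomised sensitivity analysis is confined to the motor recovery outcomes.

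**The concern.** The forms meant to show how well the device and dosage are tolerated are completed only at a visit that follows 12 weeks of treatment. A participant who leaves in week 3 because stimulation is unpleasant, the skin reacts or the home schedule is too heavy will normally supply no answer. The respondents are then selected on something close to the quantity being measured.

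The regimen is demanding: 10 home sessions a week and 22 lab sessions. The stimulation risks are listed for the CCFES and cNMES groups only, so any selection could differ between the stimulation arms and TOT. The abstract also says the trial should show whether CCFES can be delivered successfully at other sites, and tolerability is relevant to that. Because the primary efficacy sample is also restricted to treatment completers, no planned summary describes who stopped early or why.

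**Working it through.** The plan states no tolerability or withdrawal figure, so there is none to reproduce. The check has three steps.

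**1. Is there any visit at which an early leaver would be given the form?** From Experimental Flow: 3 (consent, baseline, set-up) + 11 (Visits 4–14) + 1 (mid-treatment) + 11 (Visits 16–26) + 1 (end of treatment) + 1 (3 months) + 1 (6 months) = 29. This agrees with the stated total. Therapy visits are 11 + 11 = 22, which also agrees with the text. The list is therefore complete and has no early-termination visit. The mid-treatment visit is not named as a time for the questionnaires.

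**2. How large could the bias be?** Let *d* be the share who leave before week 12 and give no answer, *c* the proportion of completers rating treatment tolerable, and *w* the proportion of leavers who would do so.

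- Rate seen from completers: *c*
- Rate in everyone: (1 − *d*)*c* + *d·w*
- Overstatement: *c* − [(1 − *d*)*c* + *d·w*] = *d*(*c* − *w*)

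All values of *d*, *c* and *w* are assumptions. The target of 132 gives 132/3 = 44 per group if allocation is equal; the documents state no ratio.

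| *d* (leavers of 44) | *c* | *w* = *c* | *w* = 50% | *w* = 0 |
|---|---|---|---|---|
| 5% (2.2) | 80% | 0 | 1.5 points | 4.0 points |
| 5% (2.2) | 90% | 0 | 2.0 | 4.5 |
| 10% (4.4) | 80% | 0 | 3.0 | 8.0 |
| 10% (4.4) | 90% | 0 | 4.0 | 9.0 |
| 15% (6.6) | 80% | 0 | 4.5 | 12.0 |
| 15% (6.6) | 90% | 0 | 6.0 | 13.5 |
| 20% (8.8) | 80% | 0 | 6.0 | 16.0 |
| 20% (8.8) | 90% | 0 | 8.0 | 18.0 |

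For example, with *d* = 10% and *c* = 90%, the rate in everyone is 0.9 × 90% + 0.1 × 50% = 86%, or 0.9 × 90% + 0 = 81% if no leaver found treatment tolerable.

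**3. Can the bias be expressed as a ratio of poor-tolerance rates?** Take 44 per arm, with either 4 leavers (2 intolerant) or 9 leavers (5 intolerant), and vary the number of completers reporting poor tolerance.

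- 2 such completers: 2/40 = 5.0% against 4/44 = 9.1% (1.8-fold); 2/35 = 5.7% against 7/44 = 15.9% (2.8-fold).
- 8 such completers: 8/40 = 20.0% against 10/44 = 22.7% (1.1-fold); 8/35 = 22.9% against 13/44 = 29.5% (1.3-fold).

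The ratio depends mainly on an assumed completer rate that the documents do not supply. The difference in percentage points is the safer scale.

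**The case against.** A reader might infer that people who leave early are never asked about discomfort or skin reactions. The documents do not support that. Risk Management asks for prompt reporting of every listed risk. The therapist spends 15 minutes at each of the 22 lab sessions observing the home exercise and dealing with problems. Diaries and device logs accumulate until a person stops, and they bear on tolerance of the home schedule. Someone leaving in week 3 would already have had several such contacts. The questionnaire is therefore not the only source of tolerability information.

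Stopping treatment is also not the same as leaving the study. The all-randomised sensitivity analysis includes participants however much treatment they received, which implies that some under-treated participants still provide outcomes. Nothing bars them from Visit 27. Placing the form at week 12 for someone who stops early is a reasonable reading of the schedule but is not spelled out. Eligibility requires intact skin and stimulated hand opening without pain, which removes some intolerance before randomisation. Finally, the document describes itself as extracted from the IRB protocol, so withdrawal or safety-reporting procedures may exist elsewhere.

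These objections stand as limits on the size and certainty of the problem, but they do not close the gap. The reporting and troubleshooting steps are there to manage risks. The text does not say that reports are tabulated by arm or that stopping reasons are recorded. Logs show how much was done, not why it stopped. Nor do these routes have the independence the protocol gives the questionnaire, which is administered by someone otherwise uninvolved with the participant.

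**Conclusion.** The point holds as a possible selection bias in a stated secondary purpose, and its priority is minor. As written, structured tolerability answers come from those who reach the week-12 visit, and nothing planned describes the rest by arm.

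Two stronger readings should be avoided. The documents do not show that tolerability is in fact overstated: they give no withdrawal rate, withdrawal reasons or questionnaire results. Nor do they support a statement that poor tolerance is understated by some fixed multiple, since the ratio moves from 2.8 to 1.1 under equally arbitrary inputs.

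The overstatement is zero if leavers and completers would answer alike. Under the assumed ranges it is 1.5 to 8 points if half of leavers found treatment tolerable, and 4 to 18 points if none did. These figures assume that every completer answers and that no early leaver does; any early stopper who still attends Visit 27 reduces them.

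The consequences are limited. The primary endpoint is change in the Box and Blocks Test at 6 months post-treatment, neither aim concerns tolerability, and no between-arm tolerability comparison is planned. This point does not address the timing of the questionnaires as efficacy outcomes.

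**What to change.** - **Protocol, Questionnaires paragraph:** state that the existing device, dose and ease-of-use items are given at week 12 or when a participant stops assigned treatment, whichever comes first. The same independent staff member would administer them, by telephone if needed, and record the main reason for stopping.
- **Statistical Analysis Plan:** add one descriptive table, by assigned arm, of tolerability answers and stopping reasons for everyone who started treatment. Show early stoppers separately, and restrict the device items to CCFES and cNMES.
- **If data collection is over**, as the past tense of the Statistical Analysis Plan suggests: label the questionnaire results as completers-only, and report withdrawals and any recorded reasons by arm.

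The cost is about one sentence in the protocol, one table, and a short call for each early stopper by staff already in the plan. Some early stoppers will decline the call, so the bias would be reduced rather than removed. The number who decline should be reported.

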Therapies for Recovery of Hand Function After Stroke

NCT03574623

Study Protocol and Statistical Analysis Plan

Note: The text below was extracted from the IRB protocol for this study, which was first approved on January 22, 2018. The most recent amendment to the protocol was approved on:

April 19, 2023

Study Protocol

Abstract

This is the first multi-site clinical trial of contralaterally controlled functional electrical stimulation (CCFES). CCFES is an innovative technology and rehabilitation therapy for improving the recovery of hand function in patients with upper extremity hemiparesis. CCFES applies electrical stimulation to the paretic finger and thumb extensor muscles through surface electrodes, causing the weak hand to open, a function that is often lost in stroke survivors. The patient controls the intensity of stimulation to their paretic hand by wearing a glove with sensors on their unaffected contralateral hand. When the patient opens their unaffected hand, a proportional intensity of stimulation opens their paretic hand. CCFES puts the patient back in control of their paretic hand, and this may drive neuroplastic changes that lead to better recovery of hand function. The central hypothesis is that CCFES is more effective for recovery of hand function than conventional cyclic neuromuscular electrical stimulation (cNMES) therapy or task oriented training (TOT) without electrical stimulation. Stroke survivors between 6 and 24 months post-stroke will be randomized to 12 weeks of CCFES, cNMES (which applies electrical stimulation to the hand extensors but with pre-set timing and intensity), or TOT without electrical stimulation. This study will determine if CCFES can be administered with positive results at other sites, will establish the clinical efficacy of CCFES (comparison with cNMES), and will generate initial estimates of effectiveness of CCFES (comparison with TOT).

Specific Aims

AIM 1. Compare the effects of CCFES and cNMES in improving hand function after stroke.

Research Hypothesis: At 6 mo post-treatment, improvements in hand function will be significantly greater after CCFES than cNMES, and a greater proportion of participants will achieve clinically significant improvements after CCFES than cNMES. Outcomes will include measures of dexterity, upper extremity activity limitation and impairment, and patient-reported outcomes.

AIM 2. Compare the effects of CCFES and TOT in improving hand function after stroke.

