The primary analysis was based on a modified intention-to-treat (ITT) sample, which included participants in the group to which they were assigned who completed the treatment phase of the study. For all measures, changes from baseline were modeled using a linear mixed effects modeling approach, which accounts for missing values using maximum likelihood estimation. The linear mixed effects model using the restricted maximum likelihood (REML) estimator was employed, along with the Satterthwaite approximation to estimate the denominator degrees of freedom. While REML assumes normality of the random effects and residuals, it is generally more robust to violations of this assumption than traditional maximum likelihood, particularly in the estimation of fixed effects. The model included a random intercept to account for individual variability, and we specified a compound symmetry covariance structure to model the within-subject correlations. Least squares mean estimates were calculated after fitting each model for each group at each timepoint and were used to quantify within-group changes from baseline and between-group differences in change from baseline to 6 mos post-treatment. Statistical significance was set at $p < 0.05$. No adjustments were made for multiple comparisons in order to maintain a balance between Type I and Type II error rates. This balanced approach to error control was prioritized rather than strictly minimizing Type I error at the expense of statistical power and increasing the risk of overlooking meaningful effects. Pair-wise Chi-square tests were used to compare responder rates between groups.

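### The only stated time for the patient-reported questionnaires is end of treatment, which conflicts with Aim 1's 6-month hypothesis and with the SAP's baseline-to-6-month model

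*Combined protocol and SAP*

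**What the plan says.** Under Specific Aims, the Aim 1 hypothesis fixes the time point: "At 6 mo post-treatment, improvements in hand function will be significantly greater after CCFES than cNMES". It then lists the outcome domains: "Outcomes will include measures of dexterity, upper extremity activity limitation and impairment, and patient-reported outcomes".

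Under Outcome Measures, the Questionnaires paragraph refers to "questionnaires including the Stroke Impact Scale Hand Section", the "Neuro-QOL Upper Extremity Function Fine Motor ADL" and a separate end-of-treatment form. It states why they are used: "The purpose is to gain insight into how well the device and dosage are tolerated and the subjects' perception of effectiveness". It gives one administration time for the group: "The questionnaires will be administered at end of treatment by a staff member who will have no other interaction with the subjects".

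The Statistical Analysis Plan sets the scope of the model: "For all measures, changes from baseline were modeled using a linear mixed effects modeling approach". It uses the fitted means to estimate "between-group differences in change from baseline to 6 mos post-treatment".

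Three other places bear on the question:
- Methods and Procedures includes a Stroke Impact Scale score among the baseline characteristics, without saying whether it covers the Hand Section.
- Outcome Measures opens with a general schedule of five blinded assessments (baseline, 6 weeks, 12 weeks, and 3 and 6 months post-treatment). It does not say whether the questionnaires belong to it.
- Experimental Flow shows that a baseline visit (Visit 2) and a 6-month visit (Visit 29) exist, at 2 hours each, but assigns no instruments to them.

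**The concern.** The hypothesis and the model both require PRO values at 6 months post-treatment, and the model also requires a baseline. The one sentence that gives the PRO scales a time names neither. A site that followed that sentence literally would collect the scales once, at week 12, and the analysis promised under Aim 1 would have nothing to work on.

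What is at stake is an outcome domain that Aim 1 names. The likely outcome would be a week-12 comparison presented under a 6-month hypothesis. A reader would then take a result at the end of treatment as evidence of durable benefit.

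**Working it through.** No arithmetic from the plan needs reproducing, and the point does not depend on sample size, power or alpha. The check compares the time points that the SAP contrast needs with those that the documents explicitly give each scale.

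| Scale | Baseline | End of treatment (12 wk) | 6 months post-treatment | Needed points stated |
|---|---|---|---|---|
| Neuro-QOL Fine Motor ADL | not stated | stated | not stated | 0 of 2 |
| SIS Hand Section | SIS score stated, section unspecified | stated | not stated | at most 1 of 2 |
| Either scale, if the general five-time-point schedule applies | yes | yes | yes | 2 of 2 |

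1. *The 6-month contrast.* It is the difference between two groups' least-squares mean changes at the 6-month visit. If no participant in any arm has a value at that visit, the group-by-visit term for it cannot be estimated. The SAP relies on maximum likelihood for missing values. That handles values missing for some participants at a visit, not a visit with no observations at all.

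2. *The change score.* Change at a visit is the value at that visit minus the baseline value. Without a Neuro-QOL baseline there is no Neuro-QOL change at any visit. For the SIS, a change from baseline to week 12 could be formed, provided the baseline score includes the Hand Section.

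3. *Which timing statement governs.* The Box and Blocks Test, Fugl-Meyer, ARAT and SULCS paragraphs carry no separate administration time, so the general schedule naturally applies to them. The Questionnaires paragraph has its own timing sentence, and a specific statement normally overrides a general one. Two further features point to a single administration. The person giving the questionnaires is to have no other contact with participants, which fits poorly with four more administrations by the same person. The stated purpose, tolerability of device and dosage, has no meaning at baseline. The timing sentence also uses the plural after a list of three instruments, so it is hard to confine to the third.

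**The case against.** The strongest case on the other side is that the paragraph is loosely drafted and the scales were in fact given throughout.
- Nothing in the paragraph says that end of treatment is the sole time.
- The paragraph sits in a section that opens with a five-time-point schedule. If that schedule covers the scales, every required value exists and the analysis is feasible.
- Only one of the three instruments is labelled as an end-of-treatment form, a label that distinguishes little if all three are given only then. The stated purpose suits that form better than scales of hand function.
- The SAP is written in the past tense. Read literally, its statement about all measures suggests that baseline and follow-up values were available for the PROs, if they are among those measures.
- The published text is an extract from the IRB protocol, so a schedule by instrument may exist elsewhere. That cannot be checked here.

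Most of this stands, and it limits the conclusion. It shows that the data may exist; it does not remove the conflict. If the scales were given at every assessment, the Questionnaires paragraph is wrong as written. If they were not, Aim 1 and the SAP promise an analysis that cannot be done. Some of these texts need correcting on either reading.

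**Conclusion.** The point holds as an internal inconsistency about timing. End of treatment is the only time the documents tie to the PRO questionnaires as a group. No 6-month PRO collection and no Neuro-QOL baseline are stated. Followed as written, the 6-month contrast would have no data for either scale, and Neuro-QOL would have no change score. This rests on reading the specific timing sentence as overriding the general schedule, which is the more natural reading but not a certain one.

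A reader might infer three stronger things that the documents do not support:
- *The PROs were collected only at end of treatment, so the analysis is impossible for all 132 planned participants.* The exclusivity is an inference, the baseline Stroke Impact Scale score tells against it, and a count of zero out of the target sample only restates the inference as a number.
- *The whole change-from-baseline model fails for PROs.* For the SIS, a change to week 12 may be available.
- *A week-12 comparison falls where participants' expectation effects are largest.* The trial is described only as assessor-blinded, so self-report is open to such effects, but nothing in the documents says how they vary over time.

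The weight is moderate. The primary endpoint, change in Box and Blocks score at 6 months post-treatment, is not affected. PROs are one of several further outcome domains.

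**What to change.** Correct the Questionnaires paragraph so that the SIS Hand Section and the Neuro-QOL scale are given at baseline and 6 months post-treatment, at the existing assessment visits. Keep only the tolerability and perception form at end of treatment. Reword the condition on the person administering the questionnaires so that it is compatible with repeated administration. State in Methods and Procedures whether the baseline Stroke Impact Scale score includes the Hand Section. If the scales were already collected on that schedule, this is a text correction only. Otherwise it is an amendment adding two short scales at 2-hour visits, with a small burden on participants.

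The past-tense SAP suggests that collection may be over. If the scales were collected only at end of treatment and the schedule can no longer change, remove PROs from the 6-month hypothesis and exempt them from the model for all measures. Report them instead as a between-group comparison at week 12, labelled as such. Adjust the SIS for its baseline if that score includes the Hand Section; Neuro-QOL would be compared without baseline adjustment. With one post-baseline value per participant, an ordinary linear model is enough, since a random intercept could not be separated from the residual. The cost is that the trial would then make no claim about lasting patient-reported benefit.
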